10.8 Early Termination and Unscheduled Visits

The handling of the early termination efficacy and safety assessments in the statistical analyses will be discussed during the Data Review Meeting and the decisions will be fully documented in the Data Review Report.

With regards to unscheduled assessments, will be evaluated case by case during the Data Review Meeting.

The following rules on data re-allocation will be considered:

- Data collected at multiple visits (spirometry, ACQ score, vital signs, laboratory data, and ECG) recorded at the study termination visit for discontinued patients will be re-allocated by selecting the next visit at which the assessment was planned. For each assessment, only the visits at which the assessment was scheduled will be considered for re-allocation. This means that ECG and laboratory data can be re-allocated only to Visit 4. For example, if the last visit performed before the study termination visit was Visit 2, the data recorded at the study termination visit will be re-allocated to Visit 3 for spirometry, ACQ score, and vital signs, and to Visit 4 for 12-lead ECG and laboratory data. If the study termination visit was performed less than 7 days after the preceding visit, then the data recorded at the study termination visit will not be re-allocated and they will be excluded from the statistical analysis.
- For discontinued patients, efficacy data recorded in the diaries from the last visit performed before the study termination visit or the date of discontinuation onwards will be reallocated to the next expected inter-visit period;
- in case of missing intermediate visit not due to the re-allocation of data collected at the study termination visit (e.g., Visit 3 missing, but Visits 2 and 4 performed), an expected date for the missing Visit 3 will be imputed in order to define the inter-visit periods for diary data. The expected date for the missing Visit 3 will be imputed as follows: Visit 3 expected date = Visit 2 date + 28 days.
- Additional unscheduled/optional assessments will be considered on a case-by-case basis and their inclusion in the analysis will be discussed at the DRM and confirmed in the DRR prior to data base lock and unblinding.
- Laboratories: the last assessment before the first randomised study medication intake of each parameter will be considered as from Visit 1 in the analysis. For WBC and the differential count parameters (lymphocytes, neutrophils, monocytes, eosinophils, basophils) the last complete assessment (i.e., with available measurements for all these parameters) before first study drug intake will be considered in the analysis. If no complete assessment is available, the last assessment before first study drug intake with the highest number of available parameters will be considered in the analysis.

Potential issues of the approach above defined and other decisions regarding data re-allocation will be evaluated during the blind review of the data and documented in the Data Review Report.

11 Table of Contents for the Tables, Listings and Figures

Key Frist Results (KFR) are identified with an “*”.

Post-Text Tables

CSR Section 14.1: Demographic data

Table 14.1.1.1: Screening Failures (All Enrolled Subjects)

* Table 14.1.1.2.1: Patient Disposition (All Randomized Subjects)

Table 14.1.1.2.2: Summary of Subjects by Visit (All Randomized Subjects)

Table 14.1.1.3.1: Major Protocol Deviations (ITT Population)

Table 14.1.1.3.2: Minor Protocol Deviations (ITT Population)

* Table 14.1.1.4.1: Summary of Analysis Sets (All Randomized Patients)

Table 14.1.1.4.2: Summary of Analysis Sets by US Region (All Randomized Patients)

Table 14.1.2.1: Demographic Characteristics (Safety Population)

Table 14.1.2.2: Demographic Characteristics (ITT Population)

Table 14.1.2.3: Demographic Characteristics (PP Population)

Table 14.1.3.1: Asthma History and Smoking Habits (Safety Population)

Table 14.1.3.2: Asthma History and Smoking Habits (ITT Population)

Table 14.1.3.3: Asthma History and Smoking Habits (PP Population)

Table 14.1.4.1: Medical and Surgical History (Safety Population)

Table 14.1.4.2: Medical and Surgical History (ITT Population)

Table 14.1.5.1: Concomitant Diseases (Safety Population)

Table 14.1.5.2: Concomitant Diseases (ITT Population)

Table 14.1.6.1: Central Spirometry at Visits 1 and 2 and Reversibility at Visit 1 (Safety Population)

Table 14.1.6.2: Central Spirometry at Visits 1 and 2 and Reversibility at Visit 1 (ITT Population)

Table 14.1.6.3: Central Spirometry at Visits 1 and 2 and Reversibility at Visit 1 (PP Population)

Table 14.1.7.1: Screening and Baseline Characteristics (Safety Population)

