4.4 Subject Withdrawals

Subjects may be discontinued from the study for any of the following reasons:

- An adverse event occurs that, in the opinion of the investigator, makes it unsafe for the subject to continue with the study drug or study procedures. In this case, the appropriate measures will be taken.
 - Subjects who experience a severe asthma exacerbation any time after screening (V1) will be instructed to visit the site as soon as possible for an Early Termination Visit and will be withdrawn permanently from the study. The Adverse Event form will be completed and appropriate medical management of the asthma exacerbation will be ensured by the study investigator, with the aim to preserve the research subject's well-being at all times.
- The subject receives systemic corticosteroid treatment
- The subject is lost to follow-up.
- The subject withdraws consent.
- The subject's safety is affected by violation of inclusion or exclusion criteria or use of non-permitted concomitant medications.
- The subject is unwilling or unable to adhere to the study requirements, i.e, non-compliance.

- The sponsor or the regulatory authorities or the Ethics Committee(s), for any reason, terminates the entire study, or terminates the study for this trial site or this particular subject.

It is understood by all concerned that an excessive rate of withdrawals can render the study uninterpretable; therefore, unnecessary withdrawals of subjects should be avoided. However, should a subject discontinue the study, all efforts will be made to complete and report the observations as thoroughly as possible.

In case of withdrawal, the Investigator must fill in the “Study Termination” page in the eCRF, reporting the main reason for withdrawal.

If a subject is withdrawn/drops-out of the study after receiving the test treatment, the subject study number and corresponding test treatments should not be reassigned to another subject.

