5.2 Non-Permitted Concomitant Medications

The following medications are not permitted during the total study period starting from Screening visit (V1). Subjects who take any of these medications during the run-in period (V1-V2) should not be randomized into the study. Subjects who take any of these medications during the randomized treatment period (V2-V4) will be carefully evaluated by the investigator for Early Withdrawal on the basis of the potential impact on efficacy or safety evaluations and in the best interest of the subject.

1. Inhaled corticosteroids other than the run-in medication and study drug
2. Inhaled short-acting muscarinic antagonists (SAMA), or long-acting muscarinic antagonists (LAMA)

3. Inhaled fixed or free combinations of ICS/LABAs
4. Inhaled long-acting β_2 -agonist drugs (LABAs)
5. Any other asthma treatments (e.g. cromolyn sodium, nedocromil sodium, leukotriene modifiers)
6. Any oral/parenteral/intramuscular (depot) corticosteroid therapy for asthma exacerbation or other medical condition
Note: any subject requiring systemic corticosteroid treatment will be discontinued from the study.
7. Xanthine derivative (e.g. theophylline)
8. Anti-IgE and anti-IL5 monoclonal antibodies
9. Tricyclic antidepressants and Monoamine oxidase inhibitors (MAOIs)
10. Systemic anticholinergics
11. Non-cardioselective β -blocking drugs (including eye drops), except if taken at stable regimen for at least 2 months before screening
12. Any drug known to prolong the QT interval (e.g. quinidine, procainamide, amiodarone), except if taken at a stable regimen for at least 2 months before screening
13. Any medication that could interact with the study drug, according to Investigator's judgment

Prior to screening spirometry (Visit 1), the following washout periods must be respected: [\[58\]](#)

Caffeinated substances	6 hours
Inhaled and/or nebulized short-acting β_2 -agonists	6 hours
Inhaled and/or nebulized short-acting muscarinic antagonists	8 hours
Inhaled combination of short-acting β_2 -agonists / short-acting muscarinic antagonists	8 hours
Inhaled corticosteroids (bid)	24 hours
Inhaled long-acting β_2 -agonists (bid)	24 hours
Inhaled fixed combinations of ICS/LABAs (bid)	24 hours
Inhaled corticosteroids (qd)	48 hours
Inhaled "ultra-long-acting" β_2 -agonists (qd)	48 hours
Inhaled fixed combinations of ICS/LABAs (qd)	48 hours
Oral leukotriene modifiers	72 hours
Inhaled LAMA	7 days
Xanthine derivatives	7 days
Ketotifen	7 days
Cromoglycate	7 days

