7.1.7 Early Termination Visit

If a subject prematurely discontinues the study after randomization, all efforts will be made to perform an early termination visit which will include the following assessments, providing there are no safety issues for the subject and in accordance with the subject's agreement:

- All study material (Study and rescue medications, subject diary) will be collected.
- **No administration of study drug will take place at the Early Termination Visit.**
- Site to update IRT.
- The ACQ questionnaire will be completed.
- Vitals signs [systolic (SBP) and diastolic (DBP) blood pressure] will be measured before spirometry, bronchodilator, or study drug administration, after 5 minutes of rest, in resting position (see [section 7.2.3](#)).
- A 12-lead ECG will be performed before spirometry and/or bronchodilator, after 5 minutes of rest (see [section 7.2.5](#)).
- The investigator will check in the electronic diary portal whether subject has been transmitting data daily since previous visit.
- Changes of concomitant medications being taken by the subject will be recorded.
- A full physical examination will be performed, including assessment of oral candidiasis.
- A blood sample will be collected, after an overnight fasting (at least 10h, when possible), for the assessments of (see [section 7.2.10](#)):
 - standard hematology and blood chemistry;
 - a serum β -HCG test in women of childbearing potential.
 - The blood samples must be collected **after vital signs and 12-lead ECG recording**.
- The occurrence of other adverse events will be checked and recorded if any.
- Spirometry: FVC spirometry measurement will be then performed to assess FEV₁ and FVC. This measurement will be taken at T -45 min and T -15 min before the expected time for the morning dose of study drug at approximately the same time as done on V2.
- The investigator will prescribe each subject an appropriate treatment or restore their initial therapy or refer them to their primary care physician.
- An appointment will be made in 1 week time for the follow-up phone call.

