7.2.9 Asthma Action Plan and Handling of Asthma Exacerbations

The subject will be instructed to contact the site immediately if they experience a severe asthma exacerbation based on the following definitions:

Severe Asthma Exacerbation[\[74\]](#)

Severe asthma exacerbations are events that require urgent action on the part of the subject and physician to prevent a serious outcome, such as hospitalization or death from asthma. The definition of a severe asthma exacerbation for clinical trials should include at least 1 of the following:

- Initiation of systemic corticosteroids (tablets, suspension, or injection), or an increase (e.g. doubling) from a stable maintenance dose, **for ≥ 3 consecutive days**.
 - For consistency, courses of corticosteroids separated by 1 week or more should be treated as separate severe exacerbations
- A hospitalization or ER visit because of asthma, requiring systemic corticosteroids.

Moderate Asthma Exacerbation[\[75\]](#)

A moderate exacerbation is defined as ≥ 1 of criteria fulfilled **and** leading to a change in treatment*:

- a) Nocturnal awakening(s) due to asthma requiring SABA for 2 consecutive nights
- b) Increase from baseline in occasions of SABA use on 2 consecutive days (minimum increase: 4 puffs/day)
- c) $\geq 20\%$ decrease in am or pm PEF from respective baseline on ≥ 2 consecutive mornings/evenings or $\geq 20\%$ decrease in FEV1 from baseline
- d) Visit to the emergency room/trial site for asthma treatment not requiring systemic corticosteroids

Subjects who experience a severe asthma exacerbation will be instructed to visit the site as soon as possible for an Early Termination Visit and will be withdrawn permanently from the study. Appropriate medical management of all asthma exacerbations will be ensured by the study investigator with the aim to preserve the research subject's well-being at all times.

**Any change in treatment should be reviewed with the subject, and all concomitant medications should be recorded in the CRF.*

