8.1.1 Rules for Handling Missing Data

Handling of missing data for the statistical analysis is described below:

For the primary efficacy analysis, a linear mixed model for repeated measures will be used to handle missing data. Under the Missing At Random (MAR) assumption, this model provides an unbiased estimate of the treatment effect that would have been observed if all subjects had continued on treatment for the full study duration. This approach addresses efficacy (or de jure) hypotheses, estimating the causal effects of the initially randomized drug if taken as directed (in contrast with effectiveness, or de facto, hypotheses, evaluating the effect of the drug as actually taken). The efficacy estimand is considered appropriate in the context of a phase II study aiming at characterizing dose-response.

The specific ways how to deal with missing data, in particular with partial or missing dates (e.g., of medication use), missing spirometry data and missing questionnaire data, is laid out in detail in the description of the variable derivation in the subsections under Section 7.2.

Other critical missing data, if any, will be discussed during the blind review of the data. Decisions will be fully documented in the Data Review Report.

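### SAP 10.8 lets termination-visit values taken after systemic corticosteroids, or well after the last dose, enter the primary model as Week 4 or Week 8 with no written exclusion criterion, against the stated on-treatment target

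*SAP*

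**What the plan says.** **The rule.** Under SAP 10.8, spirometry, ACQ and other multi-visit data "recorded at the study termination visit for discontinued patients will be re-allocated by selecting the next visit at which the assessment was planned". If Visit 2 was the last visit, the value becomes Visit 3 (Week 4). By the same rule, after Visit 3 it becomes Visit 4 (Week 8). The one stated exception is a termination visit less than 7 days after the preceding visit. The section also sends early-termination handling to the Data Review Meeting, and it closes: "Potential issues of the approach above defined and other decisions regarding data re-allocation will be evaluated during the blind review of the data".

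**The target.** SAP 8.1.1 (and Protocol 12.3.2) says the mixed model, under MAR, estimates the "treatment effect that would have been observed if all subjects had continued on treatment for the full study duration".

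**Who reaches the termination visit.** Protocol 4.4 lists among its reasons for discontinuation: "The subject receives systemic corticosteroid treatment". Protocol 7.2.9 says: "Subjects who experience a severe asthma exacerbation will be instructed to visit the site as soon as possible for an Early Termination Visit". Both limbs of its severe-exacerbation definition involve systemic corticosteroids; the second reads "A hospitalization or ER visit because of asthma, requiring systemic corticosteroids".

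**What is measured there.** Under Protocol 7.1.7, if there is no safety issue and the subject agrees, "FVC spirometry measurement will be then performed to assess" FEV1 and FVC. The ACQ is completed too. No maximum time since the last dose is given.

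**The concern.** The target is the effect under continued treatment. MAR-based modelling serves it when the values fed in are on-treatment values and the rest are missing. SAP 10.8 instead feeds in whatever was recorded at the termination visit, including readings after study drug had been stopped or systemic corticosteroids started. Such a reading does not show what the subject's FEV1 would have been on randomized treatment.

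The effect depends on the mechanism:
- Drug effect lost after stopping shrinks the active-placebo difference even when withdrawal is equal across arms, because stopping placebo removes no active drug.
- Readings raised by systemic corticosteroids shrink it if they are more frequent on placebo.
- Readings still low from an exacerbation after corticosteroids have started enlarge it if they are more frequent on placebo.

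Which of these values count in the primary result is left to case-by-case decisions, and no planned ITT table would show what those decisions did.

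**Working it through.** **1. Can such values get in?** Take a subject who stops study drug the day after Visit 3 and attends for termination three weeks later. The visit is more than 7 days after Visit 3, so its FEV1 becomes Week 8. The same holds if systemic corticosteroids were started in between. A value re-allocated to Week 4 affects Week 8 only indirectly, through the model.

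**2. Does anything else screen them out?**
- SAP 7.1 ends the randomized treatment period at the termination visit, not at the last dose.
- SAP 7.2.10 has a spirometry rule for rescue medication and keeps those data in the ITT analysis. It has no rule for systemic corticosteroids.
- SAP 7.2.10 also lets the Blind Data Review Meeting exclude spirometry values, which are then set to missing. It gives technical issues as an example and no criterion for this case.
- Protocol 5.2 forbids "corticosteroid therapy for asthma exacerbation or other medical condition", and SAP 6.1 lists non-permitted medication as a major deviation. The PP repeat may therefore remove many post-steroid values.
- Stopping drug is not a listed deviation, and compliance in SAP 7.2.8 counts doses only up to the last intake. Off-drug values are therefore not isolated.
- The two ITT sensitivity analyses in SAP 8.2 change the ICS stratum and the spirometry grade, not re-allocation.

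**3. The plan's own figures** (Protocol 12.1). With 200 mL, SD 430 mL and two-sided alpha 0.05/3 = 0.0167, noncentral t gives 79.9% power at 98 per group and 80.4% at 99. 99/0.85 = 116.5, so 117 per group and 585 in all. These reproduce. With 117 per arm, SE = 430 × √(2/117) = 56 mL.

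**4. Illustrative shift at Week 8.** Shift = f_active × d_active − f_placebo × d_placebo, where f is the share of the arm with an affected value and d is its mean deviation. The rates and deviations are assumptions. The 15% is borrowed from the protocol's non-evaluable rate as an upper reference. Half of the withdrawals are taken as affected.

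| Case | Shift (mL) | Estimate |
|---|---|---|
| Off drug, d_active −200, 15% per arm | 0.075 × (−200) = −15 | 185 |
| Off drug, 10% per arm | 0.05 × (−200) = −10 | 190 |
| Off drug, 5% per arm | 0.025 × (−200) = −5 | 195 |
| Off drug, d_active −100, 15% per arm | 0.075 × (−100) = −7.5 | 192.5 |
| Steroid-raised +300, placebo 15%, active 5% | 0.025 × 300 − 0.075 × 300 = −15 | 185 |
| Still low −300 after steroids started, 15% vs 5% | 0.025 × (−300) − 0.075 × (−300) = +15 | 215 |

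Steroid-raised readings at equal rates give no shift. If all withdrawals are affected, the shifts double.

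**5. Simulation check.** Two arms of 117, two visits, assumed visit correlation 0.7, true effect 200 mL, withdrawal after Visit 3, 3000 replicates. The termination reading is the midpoint of the subject's Week 4 and Week 8 values plus the deviation. With random withdrawal the current rule gives 185, 189, 193, 192, 185 and 215 mL for the six rows. Leaving affected values missing gives 198 to 202.

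**6. Withdrawal driven by low Week 8 FEV1** (estimates for half / all affected):

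| Case | Current rule | Affected left missing |
|---|---|---|
| Off drug, 15% per arm | 184 / 169 | 199 / 200 |
| Off drug, 15% vs 5% | 188 / 185 | 184 / 173 |
| Steroid +300, 15% vs 5% | 179 / 163 | 185 / 172 |
| Low −300, 15% vs 5% | 210 / 225 | 185 / 172 |

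With unequal withdrawal, leaving affected values missing is further from 200 mL in 4 of 6 cells. Re-allocating nothing gives 170 to 173.

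**7. Scale.** 15/56 = 0.27 of one SE. By normal approximation, a fall from 200 to 185 mL takes power from 81% to 74% with 99 readings per arm. With 117 it goes from 88% (200/56.2 − 2.39 = 1.16) to 82% (185/56.2 − 2.39 = 0.90).

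**The case against.** **Blind review already offers a way out.** The SAP 10.8 rules are worded as rules to be considered. SAP 7.2.10 can set excluded spirometry to missing and flags it in the listings. Protocol 12.3 lets the SAP be updated before the blind is broken. The decisions are blinded and documented, so this answers any worry about steering by treatment. It does not supply a criterion, and the written default still conflicts with the written target.

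**Keeping termination readings can be the better choice.** They carry information on subjects who do badly, and deleting them leans harder on MAR. Since the protocol withdraws severe exacerbators, withdrawal linked to poor control is plausible. This stands, as step 6 shows, and it is why the repair cannot rest on the revised rule alone.

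**Frequency and size are assumed.** This also stands. The 15% is not a withdrawal rate, and the affected share has no source in the documents. The visit after a severe exacerbation is meant to be prompt, spirometry there is conditional, and Protocol 1 says asthma stability may last several days or longer after corticosteroids stop. Full loss of 200 mL in every withdrawal is extreme.

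**The PP repeat covers the steroid limb in part.** True. Its exact deviations are fixed at blind review, so excluding early stoppers is possible too. The primary analysis, however, is ITT.

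**Stronger readings to avoid.** A reader might infer that re-allocation biases the primary result in a known direction, or that every termination reading should be dropped. The documents support neither. The sign depends on mechanism and on withdrawal by arm, which they do not give. A low reading taken on drug and before any systemic corticosteroid fits the stated target.

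**Conclusion.** The point holds for two kinds of termination-visit value: those recorded after systemic corticosteroids were started, and those recorded well after the last study drug intake. By default both can enter the primary ITT model as Week 4 or Week 8, contrary to the SAP's own target. The blind review may exclude them, but on no written criterion, and no planned ITT analysis varies the re-allocation. The same rule governs FVC and ACQ-7, for which no size was worked out.

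The textual conflict is certain; its size and direction are not derivable. Under the assumed rates (up to 15% withdrawal, half affected, deviations of 100 to 300 mL) the shift is about 5 to 15 mL either way, at most about a quarter of one SE. That is modest, but it falls on the primary result and is cheap to settle before unblinding. The case rests on matching the analysis to its stated target and showing its sensitivity, not on the revised rule being less biased in general.

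**What to change.** Before unblinding, amend SAP 10.8 for the primary model and the matching FVC and ACQ-7 models:
- Leave a termination-visit value missing, under the SAP's MAR assumption, if it was recorded (i) after systemic corticosteroids were started, or (ii) more than a pre-specified number of days after the last study drug intake. The sponsor should choose and justify that number; given the statement in Protocol 1, one missed dose need not exclude a reading.
- State how same-day starts and incomplete dates are resolved.
- Re-allocate all other termination values as now.
- Add two ITT sensitivity analyses of the primary endpoint: the current re-allocation rule, and no re-allocation.
- Report the numbers of re-allocated and excluded values by arm.

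**Cost.** SAP wording, a dataset flag with its date rules, and a few extra tables. The SAP already uses last-intake dates (7.1) and medication start dates (7.2.5). At 15% withdrawal with half affected, about 0.15 × 234 × 0.5 ≈ 18 values in two arms are left missing, and the SE rises from about 56 to 57 mL. If half of the withdrawals precede Visit 3, about 9 of those 234 subjects have no post-randomization FEV1 and leave the model under SAP 8.1, and the SE is about 58 to 59 mL.

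**Downside.** More reliance on MAR. If low FEV1 drives unequal withdrawal, the revised rule can be further from the true effect than the current one, so the primary result and the two sensitivity results should be read together.

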7.1.5 Visit 4 (Week 8 of Treatment Period)

The Visit 4 will start in the morning (before 9:00 am).

If caffeine has been ingested, or rescue albuterol has been inhaled in the previous 6 hours, or the study drug has been taken on the morning of the visit (before spirometry), or the washout for non-permitted medications has not been respected, the visit needs to be re-scheduled to take place within 2 days. Only one re-scheduling is allowed. If any of these relevant washouts is not respected again on the morning of the re-scheduled visit, the subject will be discontinued and Early Termination Visit performed and recorded in the IRT and eCRF.

The following pre-dose procedures will be performed:

- The ACQ questionnaire will be completed.
- Vitals signs [systolic (SBP) and diastolic (DBP) blood pressure] will be measured before spirometry, bronchodilator, or study drug administration, after 5 minutes of rest, in resting position (see [section 7.2.3](#)).
- A 12-lead ECG will be performed before spirometry, bronchodilator, or study drug administration, after 5 minutes of rest (see [section 7.2.5](#)).
- The investigator will check in the electronic diary portal whether subject has been transmitting data daily since Visit 3.
- Changes of concomitant medications being taken by the subject will be recorded. In case of intake of any non-permitted concomitant medication, the subject will be withdrawn from the study and recorded as Early Termination in the IRT. (see [section 5.2](#)).
- A full physical examination will be performed, including assessment of oral candidiasis.
- 24-hour urine sample will be processed for 24-hour urine cortisol and creatinine
- A blood sample will be collected, after an overnight fasting (at least 10h), for the assessments of (see [section 7.2.10](#)):
 - standard hematology and blood chemistry;
 - a serum β -HCG test in women of childbearing potential.

The blood samples must be collected **after vital signs and 12-lead ECG recording**.

In case of non-interpretable data, another determination must be performed as soon as possible and prior to the follow up safety phone call (V5).

- The occurrence of other adverse events will be checked and recorded if any.
- Pre-dose spirometry: FVC pre-dose spirometry measurement will be then performed to assess FEV₁ and FVC. This measurement will be taken at T -45 min and T -15 min before the expected time for the morning dose of study drug at approximately the same time as done on V2.

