Inter-visit periods will be used in the analysis of the average number of rescue medication, the percentage of rescue medication-free days, the percentage of asthma symptoms-free days and of asthma control day, the daily asthma symptoms scores and the morning and evening average pre-dose PEF. The periods used in these analyses are:

- Run-in Period: The Run-In Period starts at Visit 1 and runs through morning assessment of the date of Start of the Randomized Treatment Period.

- Inter-visit Period 1: Inter-visit Period 1 starts on the evening assessment of the date of the Start of the Randomized Treatment Period and runs through the morning assessment on the date of Visit 3. If the subject withdraws prematurely after Visit 2 and before Visit 3 any value collected from Visit 2 until the End of the Randomized Treatment Period will be considered for the Inter-visit Period 1. By default Inter-visit Period 2 is missing.
- Inter-visit Period 2: Inter-visit Period 2 starts on the evening assessment of the day the subject returns to the clinic at Visit 3 and runs through the morning assessment of the date of Visit 4.

If the subject withdraws prematurely after Visit 3 and before Visit 4 any value collected from Visit 3 until the End of the Randomized Treatment Period will be considered for the Inter-visit Period 2.

Date of first/last study drug intake

Date of first randomized study drug intake is derived as the minimum of 'Date/Time of administration' between the 4 inhalations (puffs) of the Morning Dose collected on the 'Study drug administration at the clinic' eCRF page. While subjects randomized to open-label QVAR® will only receive 1 inhaler, patients are required to take 2 inhalations of the content of 1 inhaler on site, the morning of Visit 2. For these patients, no minimum is required, since only 1 time is recorded.

Note: The date and time of drug administration at each visit are mandatory variables to be reported in the CRF; no missing or partial data can be accepted. Only CRF data will be considered for the date of first randomized study drug intake.

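### SAP 10.8 re-allocates termination-visit data by visit order, so after a missed Visit 3 an FEV1 measured near Week 8 is labelled Week 4 unless the blind review changes it

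*SAP*

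**What the plan says.** SAP 10.8 covers data recorded at the termination visit of discontinued subjects. These data "will be re-allocated by selecting the next visit at which the assessment was planned". The worked example shows what this means. It takes the case "if the last visit performed before the study termination visit was Visit 2, the data recorded at the study termination visit will be re-allocated to", and the destination then depends on the type of assessment: "Visit 3 for spirometry, ACQ score, and vital signs, and to Visit 4 for 12-lead ECG and laboratory data". There is one timing condition, and it is a lower limit: "If the study termination visit was performed less than 7 days after the preceding visit", the data are not re-allocated and are left out of the analysis. No upper limit is given.

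For the same subjects, diary data from the last visit performed onward "will be reallocated to the next expected inter-visit period". SAP 7.1 agrees with this for a subject who withdraws after Visit 2 and before Visit 3. All values up to the end of the treatment period go to Inter-visit Period 1, and "By default Inter-visit Period 2 is missing".

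SAP 10.8 also has a rule based on study day. It applies "in case of missing intermediate visit not due to the re-allocation of data collected at the study termination visit" and sets an expected Visit 3 date of Visit 2 + 28 days for dividing the diary data. Its example is a subject with Visit 3 missing but Visit 4 performed.

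The section opens by leaving the handling of early-termination data to the Data Review Meeting. It closes by sending any problems with these rules to the blind review, to be recorded in the Data Review Report.

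**The concern.** The label depends on which visits the subject attended, not on when the measurement was made. A subject who misses Visit 3 and has a termination visit around Day 57 contributes that FEV1 as a Week 4 value and has nothing at Week 8, the primary time point. Had the same subject attended Visit 3 on Day 29, the same FEV1 would be labelled Week 8. Within that one termination visit, spirometry would be reported at Week 4 and the ECG and laboratory results at Week 8.

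The model in SAP 8.2 has two visit levels and an unstructured covariance. A mistimed value therefore enters the Week 4 secondary analysis directly. It also informs the Week 8 estimate as if it were a Week 4 response. SAP 8.1.1 aims at the effect had every subject stayed on treatment for the full duration. An on-treatment FEV1 on Days 55-59 is direct evidence on that effect, but the rule puts it at another time point.

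**Working it through.** **Inputs.** Day 1 is the first dose and there is no Day 0 (SAP 7.1), so Week 4 is Day 1 + 28 = Day 29 and Week 8 is Day 1 + 56 = Day 57. The Visit 4 window of ±2 days (study schedule) gives Days 55-59. A diary day is an evening session plus the next morning's session (SAP 7.2.10). Termination on Day d therefore leaves d − 1 diary days after Visit 2. A split at Visit 2 + 28 days would put 28 of these in Period 1 and d − 29 in Period 2.

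**Rule applied to a discontinued subject with no Visit 3**

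| Termination day | Days from Day 29 | Days from Day 57 | SAP label for FEV1 | Nearer visit | Diary days, Period 1 / 2, discontinuation rule | Period 1 / 2 with +28-day split |
|---|---|---|---|---|---|---|
| 36 | +7 | −21 | Week 4 | Week 4 | 35 / 0 | 28 / 7 |
| 43 | +14 | −14 | Week 4 | tie | 42 / 0 | 28 / 14 |
| 44 | +15 | −13 | Week 4 | Week 8 | 43 / 0 | 28 / 15 |
| 50 | +21 | −7 | Week 4 | Week 8 | 49 / 0 | 28 / 21 |
| 55 | +26 | −2 | Week 4 | Week 8 | 54 / 0 | 28 / 26 |
| 57 | +28 | 0 | Week 4 | Week 8 | 56 / 0 | 28 / 28 |
| 59 | +30 | +2 | Week 4 | Week 8 | 58 / 0 | 28 / 30 |

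From Day 44 the label is the more distant visit. On Days 55-59 the value lies inside the Visit 4 window itself. Where Period 2 is missing, the derived whole-period diary values are missing too, because SAP 7.2.10 requires both periods.

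**Can it happen?** The +28-day rule shows that the SAP expects some missed Visit 3s. In Arms A-D each canister holds 120 doses and is used twice a day, so the Visit 2 box lasts 120 / 2 = 60 days. In Arm E four actuations a day give 240 / 4 = 60 days if two packs are dispensed (Protocol 6.2.3.2), but 120 / 4 = 30 days if one is (Protocol 6.3.3). Those two sections need to be reconciled. Protocol 7.1.5 also gives a route to a termination visit near Day 57. After a second washout failure at the rescheduled Visit 4, "the subject will be discontinued and Early Termination Visit performed and recorded in the IRT and eCRF".

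**Effect on power.** The plan's own figure first: a difference of 200 mL, SD 430 mL and two-sided alpha 0.0167 need 99 per group for 80% power by the noncentral t (power 0.804), which matches the SAP. Then 99 / 0.85 = 116.5, rounded up to 117, and 5 × 117 = 585. By the normal approximation, power = Φ(200 / (430 × √(2/n)) − 2.39), which is 0.810 at n = 99. Suppose k of the 99 Week 8 values per group are lost and contribute nothing. The documents give no k, so the values below are assumptions:

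- k = 1: 0.806
- k = 2: 0.801
- k = 3: 0.797
- k = 5: 0.787

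The noncentral t gives values about 0.007 lower throughout.

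**The case against.** The strongest reply is that these rules are not final. SAP 10.8 says that they will be considered, and it refers potential issues to the blind review. A Day 57 FEV1 mapped to Week 4 is the kind of issue that such a review could catch. This stands as a limit on the point: the mislabelling is what the stated rule produces, not a settled outcome. But the blind review only permits a repair. It does not say what the repair is, and the rule feeds the primary endpoint.

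The general sentence, read alone, might mean the next visit by calendar. The worked example rules this out.

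On the diary data the objection has more force. A Visit 3 that was never attended was arguably not made missing by re-allocation, and the case with Visit 4 performed is only an example. The +28-day split might therefore be meant to cover discontinued subjects. SAP 7.1 does not say whether withdrawal before Visit 3 refers to the planned date or to the performed visit. Against this, the bullet on discontinued subjects' diaries points to Period 1. A reader might infer that the SAP flatly refuses the split to these subjects, but the text is only unclear.

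A reader might also infer that identical measurements get different labels solely because of the form on which they are recorded. The route in Protocol 7.1.5 does not show that, because a termination visit reached after two washout failures is not equivalent to a valid Visit 4. It remains true that SAP 7.2.10 keeps spirometry taken after rescue medication in the ITT analysis.

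**Conclusion.** The point holds in a limited form. As written, the rule gives the wrong time point for FEV1, ACQ-7 and vital signs when a discontinued subject has no Visit 3 and terminates on Day 44 or later. The case is clearest on Days 55-59, inside the Visit 4 window. Days 44-54 are only nearer to Week 8 than to Week 4.

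Three stronger conclusions are tempting and not supported:

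- **That the subject drops out of the primary analysis.** The Week 8 cell is empty, but the subject stays in the model through the mistimed value.
- **That the number affected can be read from the 15% in the sample-size section.** That figure is a non-evaluable rate, not a withdrawal rate, and the documents do not say how many withdrawals lack a Visit 3 or come after Day 43. The 15% also already allows for losses in reaching 99 per group.
- **That the treatment comparison is biased in a known direction.** Withdrawals may well cluster in subjects losing asthma control, but nothing in the documents quantifies this.

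The number affected is probably small. On the assumed losses of 1 to 3 Week 8 values per group, power stays at about 0.80. The priority is minor. The reason to act is that the SAP already contains most of the solution and stops short of applying it clearly to these subjects.

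**What to change.** Amend SAP 10.8 before unblinding, for discontinued subjects with no Visit 3:

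- State that the expected Visit 3 date (Visit 2 + 28 days) applies to them as well.
- Re-allocate termination-visit spirometry, ACQ-7 and vital signs to whichever of Visit 3 or Visit 4 is nearer by study day: up to Day 43 to Visit 3, from Day 44 to Visit 4. Day 43 is the midpoint and is a convention, since the documents define no analysis windows. At the least, Days 55-59 should go to Visit 4.
- Split diary and PEF data at the expected Visit 3 date, under the existing 7-day minimum, and align SAP 7.1 with this.
- Leave the other re-allocation conditions unchanged.

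The cost is about one sentence in the SAP and a small change to the visit-mapping code, with no new data. There is one small loss. For termination on Days 30-35, Period 2 would hold d − 29 = 1 to 6 diary days, which is below the minimum, so those days would drop out.
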